### **7.2.4 Eastern Cooperative Oncology Group (ECOG) Performance Scale**

The investigator or qualified designee will assess ECOG status at screening and at the end of therapy study visit as specified in the Trial Flow Chart (Section 6.0).

## **7.3 Laboratory Safety Evaluations**

Laboratory tests for hematology, chemistry, and others are specified in Table 3. The total amount of blood to be drawn over the course of the trial (from pre-trial to post-trial visits), including approximate blood by visit and by sample type per subject can be found in the Procedures Manual.

**Table 3 Laboratory Tests**

Hematology	Chemistry	Correlatives
Hematocrit	Creatinine	miR21
Hemoglobin	Alkaline phosphatase	IGF-1

Platelet count	Alanine aminotransferase (ALT)	IGF-BP3
WBC (total and differential)	Aspartate aminotransferase (AST)	ESR
Red Blood Cell Count	Total Bilirubin	Adiponectin
Absolute Neutrophil Count		Leptin
		IGF-1R
		Exosome profile
		Metabolomics profile

Screening laboratory tests should be performed within 28 days prior to enrollment. Results must be reviewed by the investigator or qualified designee and found to be acceptable prior to enrollment on this treatment trial.

### 7.3.1 Correlative Studies

Serum studies as described above will be drawn anytime during the screening period and/up to Week 1 Day 1 and at the time of surgical resection.

## 8 Safety Evaluations

### 8.1 Specification of Safety Parameters

#### 8.1.1 Unanticipated Problems

Unanticipated problems (UAPs) include, in general, any incident, experience, or outcome that meets the following criteria:

- unexpected in terms of nature, severity, or frequency given (a) the research procedures that are described in the protocol-related documents, such as the IRB-approved research protocol and informed consent document; and (b) the characteristics of the participant population being studied;

UAPs are considered to pose risk to participants or others when they suggest that the research places participants or others at a greater risk of harm (including physical, psychological, economic, or social harm) than was previously known or recognized.

#### 8.1.2 Adverse Events

An adverse event is any untoward or unfavorable medical occurrence in a human participant, including any abnormal sign (for example, abnormal physical exam or laboratory finding), symptom, or disease, temporally associated with the participant's participation in the research, whether or not considered related to the participant's participation in the research.

#### 8.1.5 Serious Adverse Event (SAE)

A serious adverse event (SAE) is one that meets one or more of the following criteria:

- Results in death
- Is life-threatening (places the participant at immediate risk of death from the event as it occurred)

- Is disabling or incapacitating
- Results in inpatient hospitalization or prolongation of existing hospitalization
- Results in a persistent or significant disability or incapacity
- Results in a congenital anomaly or birth defect
- An important medical event that may not result in death, be life threatening, or require hospitalization may be considered an SAE when, based upon appropriate medical judgment, the event may jeopardize the participant or may require intervention to prevent one of the outcomes listed in this definition.

## 8.2 Safety Assessment and Follow-Up

The PI will follow adverse events with start dates occurring any time after study drug administration until 7 (for non-serious AEs) or 30 days (for SAEs) after the last day of study participation. At each study visit, the investigator (or designee) will inquire about the occurrence of AE/SAEs since the last visit. Events will be followed for outcome information until resolution or stabilization.

## 8.3 Recording Adverse Events

The following subsections detail what information must be documented for each adverse event occurring during the time period specified in Section **Error! Reference source not found.**  
**Error! Reference source not found..**

### 8.3.1 Relationship to Study Intervention

The relationship to study intervention or study participation must be assessed and documented for all adverse events. Evaluation of relatedness must consider etiologies such as natural history of the underlying disease, concurrent illness, concomitant therapy, study-related procedures, accidents, and other external factors.

The following guidelines are used to assess relationship of an event to study intervention:

1. Related (Possible, Probable, Definite)
  - a. The event is known to occur with the study intervention.
  - b. There is a temporal relationship between the intervention and event onset.
  - c. The event abates when the intervention is discontinued.
  - d. The event reappears upon a re-challenge with the intervention.
2. Not Related (Unlikely, Not Related)
  - a. There is no temporal relationship between the intervention and event onset.
  - b. An alternate etiology has been established.

### 8.3.2 Expectedness

The PI is responsible for determining whether an AE is expected or unexpected. An AE will be considered unexpected if the nature, severity, or frequency of the event is not consistent with the risk information previously described for the intervention. Risk information to assess expectedness can be obtained from preclinical studies, the investigator's brochure, published medical literature, the protocol, or the informed consent document.

### 8.3.3 Severity of Event

Adverse events will be graded for severity according to the Common Terminology Criteria for Adverse Events (CTCAE) version 4.03. Any adverse event that changes CTCAE grade over the course of a given episode will have each change of grade recorded on the adverse event case report forms/worksheets (Table 4).

**Table 4 Evaluating Adverse Events**

V4.03 CTCAE Grading	Grade 1	Mild; asymptomatic or mild symptoms; clinical or diagnostic observations only; intervention not indicated.
	Grade 2	Moderate; minimal, local or noninvasive intervention indicated; limiting age-appropriate instrumental ADL.
	Grade 3	Severe or medically significant but not immediately life-threatening; hospitalization or prolongation of hospitalization indicated; disabling; limiting self-care ADL.
	Grade 4	Life threatening consequences; urgent intervention indicated.
	Grade 5	Death related to AE
Seriousness	
A serious adverse event is any adverse event occurring at any dose or during any use of metformin or doxycycline product that:
 
†Results in death; or
 
†Is life threatening; or places the subject, in the view of the investigator, at immediate risk of death from the event as it occurred (Note: This does not include an adverse event that, had it occurred in a more severe form, might have caused death.); or
 
†Results in a persistent or significant disability/incapacity (substantial disruption of one's ability to conduct normal life functions); or
 
†Results in or prolongs an existing inpatient hospitalization (hospitalization is defined as an inpatient admission, regardless of length of stay, even if the hospitalization is a precautionary measure for continued observation. (Note: Hospitalization [including hospitalization for an elective procedure] for a preexisting condition which has not worsened does not constitute a serious adverse event.); or
 
†Is a congenital anomaly/birth defect (in offspring of subject taking the product regardless of time to diagnosis); or
 
Is a new cancer; (that is not a condition of the study) or
 
Is an overdose (whether accidental or intentional). Any adverse event associated with an overdose is considered a serious adverse event. An overdose that is not associated with an adverse event is considered a non-serious event of clinical interest and must be reported within 24 hours.
 
Other important medical events that may not result in death, not be life threatening, or not require hospitalization may be considered a serious adverse event when, based upon appropriate medical judgment, the event may jeopardize the subject and may require medical or surgical intervention to prevent one of the outcomes listed previously (designated above by a †).
	
Duration	Record the start and stop dates of the adverse event. If less than 1 day, indicate the appropriate length of time and units	
Action taken	Did the adverse event cause the metformin or doxycycline product to be discontinued?	
	Exposure	Is there evidence that the subject was exposed to the Merck product such as: reliable history, acceptable compliance assessment (pill count, diary, etc.), expected pharmacologic effect, or measurement of drug/metabolite in bodily specimen?
	Time Course	Did the AE follow in a reasonable temporal sequence from administration of the metformin or doxycycline? Is the time of onset of the AE compatible with a drug-induced effect (applies to trials with investigational medicinal product)?
	Likely Cause	Is the AE not reasonably explained by another etiology such as underlying disease, other drug(s)/vaccine(s), or other host or environmental factors

### 8.3.4 Intervention

Any intervention implemented to treat the adverse event must be documented for all adverse events.

## 8.4 Safety Reporting

### 8.4.1 Reporting to IRB

#### 8.4.1.1 Unanticipated Problems

All incidents or events that meet criteria for unanticipated problems (UAPs) as defined in Section 8.1.1 Unanticipated Problems require the creation and completion of an unanticipated problem report form (OHR-20).

UAPs that pose risk to participants or others, and that are not AEs, will be submitted to the IRB on an OHR-20 form via the eazUP system within 5 working days of the investigator becoming aware of the event.

UAPs that do not pose risk to participants or others will be submitted to the IRB at the next continuing review.

#### 8.4.1.2 Adverse Events

Grade 1 AEs will be reported to the IRB at continuing review.

Grade 2 AEs will be reported to the IRB at the time of continuing review.

#### 8.4.1.3 Serious Adverse Events

SAEs will be reported to the IRB on OHR-10 forms via the electronic reporting system (eSAEy) according to the required time frames described below.

Grade 3-4 AEs that are unexpected and deemed to be at least possibly related to the study will be reported to the IRB within 2 working days of knowledge of the event.

Grade 3-4 AEs that are deemed unrelated to the study will be reported to the IRB within 5 working days.

Grade 5 AEs will be reported to the IRB within one working day of knowledge of the event.

All SAEs will be submitted to the IRB at continuing review, including those that were reported previously.

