### 8.4.2 Reporting to SKCC DSMC

All AEs and SAEs, safety and toxicity data, and any corrective actions will be submitted to the DSMC per the frequency described in the SKCC DSMP. The report to the SKCC DSMC will also include any unanticipated problems that in the opinion of the PI should be reported to the DSMC.

For expedited reporting requirements, see table below:  
AE/SAE Reporting Requirements

DSMC

	Grade 1	Grade 2		Grade 3				Grades 4 and 5
	Unexpected and Expected	Unexpected	Expected	Unexpected		Expected		Unexpected and Expected
				With Hospitalization	Without Hospitalization	With Hospitalization	Without Hospitalization	
Unrelated Unlikely	Reviewed at Quarterly DSMC Meeting and IRB Annual Review	Reviewed at Quarterly DSMC Meeting and IRB Annual Review	Reviewed at Quarterly DSMC Meeting and IRB Annual Review	5 Working Days	Reviewed at Quarterly DSMC Meeting and IRB Annual Review	5 Working Days	Reviewed at Quarterly DSMC Meeting and IRB Annual Review	Phase I - 48 Hours (Death: 24 Hours) Phase II - 5 working days
Possible Probably Definite	Reviewed at Quarterly DSMC Meeting and IRB Annual Review	Reviewed at Quarterly DSMC Meeting and IRB Annual Review	Reviewed at Quarterly DSMC Meeting and IRB Annual Review	48 Hours (Death: 24 Hours)	Phase I - 48 Hours Phase II - 5 working days	48 Hours (Death: 24 Hours)	Reviewed at Quarterly DSMC Meeting and IRB Annual Review	Phase I and Phase II - 48 Hours (Death: 24 Hours)

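### Expedited reporting to the IRB and DSMC is keyed to CTCAE grade, so a serious, unexpected, possibly drug-related Grade 1-2 event has no expedited time frame

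*Combined protocol and SAP*

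**What the plan says.** Seriousness is defined by outcome in two places. Section 8.1.5 lists, among other criteria, "Results in inpatient hospitalization or prolongation of existing hospitalization", and also allows important medical events to count. Table 4 counts any inpatient admission, however short and even if only for observation, and any adverse event that accompanies an overdose. Neither definition refers to CTCAE grade.

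The reporting rules use grade:

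- **8.4.1.2 (IRB).** Grade 1 events go to continuing review. For Grade 2, "Grade 2 AEs will be reported to the IRB at the time of continuing review". Neither line excepts serious events.
- **8.4.1.3 (IRB).** "SAEs will be reported to the IRB on OHR-10 forms via the electronic reporting system (eSAEy) according to the required time frames described below". The list then names Grade 3-4 events that are unexpected and "at least possibly related to the study will be reported to the IRB within 2 working days of knowledge of the event"; next, "Grade 3-4 AEs that are deemed unrelated to the study will be reported to the IRB within 5 working days"; and Grade 5 events, due in one working day. The only remaining line submits all SAEs at continuing review.
- **8.4.2 table (DSMC).** Every Grade 1 and Grade 2 cell, including Grade 2 unexpected with a possible, probable or definite relationship, reads "Reviewed at Quarterly DSMC Meeting and IRB Annual Review". Hospitalization changes the timing only within Grade 3.

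**The concern.** The protocol promises time frames for SAEs and then supplies them only from Grade 3 upward. By its own definitions an SAE can be Grade 1 or 2. Staff who follow 8.4 as written would hold such an event for the next periodic review even if it were unexpected and thought to be caused by the drugs, while sending an unrelated Grade 3 admission within a week.

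Safety and tolerability is a secondary objective (2.1.2), and 1.4.1 says significant clinical benefit to participants is unlikely, so prompt committee notice of an unexpected drug-related serious event matters. The numerical safety rules would not pick it up either: the stopping table in 10.6 counts Grade 3 or higher toxicities, and 8.5 concerns Grade 4 or above.

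**Working it through.** This is mainly a comparison of text; the plan gives no figure to reproduce. Three events are traced through 8.4.

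| Event | To the IRB | To the DSMC (8.4.2 table) |
|---|---|---|
| A. Grade 2, unexpected, possibly related, precautionary admission (an SAE under 8.1.5 and Table 4) | Continuing review (8.4.1.2; no matching time frame in 8.4.1.3) | Quarterly meeting |
| B. Grade 3, unrelated, with hospitalization | 5 working days (8.4.1.3) | 5 working days |
| C. Grade 3, unexpected, possibly related, with hospitalization | 2 working days (8.4.1.3) | 48 hours |

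A is related and serious, yet reaches both committees later than B, which is unrelated. A and C differ only in grade.

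**Other routes.**

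1. Unanticipated problems. Any event meeting the 8.1.1 criteria needs a report form, but the 5-working-day clock in 8.4.1.1 is limited: "UAPs that pose risk to participants or others, and that are not AEs, will be submitted to the IRB". No clock is given for unanticipated problems that are adverse events. Section 8.4.2 adds unanticipated problems to the DSMC report at the PI's discretion, again without a clock.
2. Section 13.7. The lead site or medical monitor assesses adverse event data continuously and reviews SAEs as reports arrive. No deadline is set, and nothing there passes the event to the IRB or DSMC.
3. Overdose. Table 4 says an overdose without an adverse event "is considered a non-serious event of clinical interest and must be reported within 24 hours", but names no recipient. An overdose with a Grade 1-2 adverse event is an SAE under the same table and has no expedited time frame.

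**Size of the delay.** Assume that continuing review is annual (as the table's wording suggests), that quarterly means every 3 months, and that accrual is even. The inputs are 46 patients (Required Enrollment) and 36 months (Estimated Time to Complete Enrollment).

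- Accrual: 46 / 36 = 1.28 patients per month.
- Longest wait for the DSMC: 3 months, or 1.28 x 3 = 3.8 further enrolments.
- Longest wait for the IRB: 12 months, or 1.28 x 12 = 15.3 further enrolments (15.3 / 46 = 33% of the trial).
- If events fall evenly between reviews, the mean wait is half of each: 1.5 months (1.9 enrolments) and 6 months (7.7 enrolments).

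**The case against.** The strongest case against the point is that little slips through in practice, and much of that case stands.

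- **Grading absorbs most SAEs.** Table 4 places medically significant events, and those for which admission is indicated, in Grade 3, life-threatening events in Grade 4 and deaths in Grade 5. Most seriousness criteria therefore already imply Grade 3 or higher. What remains is chiefly precautionary admissions and overdose with a mild adverse event. This narrows the point but does not remove it.
- **Someone does see the events.** A reader might infer that nobody able to stop the study would learn of such an event until many more patients had been treated. The documents do not support that. Section 13.7 provides ongoing assessment, and the lead site, sponsor or PI can close accrual. What is late is notice to the IRB and DSMC.
- **The delays are maxima.** A reader might also infer that about 15 patients would be enrolled before any committee review. The quarterly DSMC meeting comes first, so the bound there is about 4.
- **The overdose comparison is weak.** It is tempting to call the 24-hour line a second inversion. Because it names no recipient, it cannot be set directly against an IRB or DSMC time frame. It supports a request to reconcile the two overdose provisions, and no more.
- **The SKCC DSMP is not in the documents** and may add rules for the DSMC. However, 8.4.2 points to its own table for expedited reporting, and nothing in the documents suggests that the DSMP would change the IRB wording in 8.4.1.2 and 8.4.1.3.

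**Conclusion.** The point holds in this form. Sections 8.4.1.2 and 8.4.1.3 and the 8.4.2 table give no expedited IRB or DSMC time frame to a Grade 1-2 event that is serious, unexpected and at least possibly related, and they rank it behind an unrelated Grade 3 event with hospitalization. The wait is at most about 12 months for the IRB, against 2 working days for a like Grade 3 event, and at most about 3 months for the DSMC, against 48 hours for a like Grade 3 event with hospitalization.

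This rests on a literal reading of 8.4, on annual and quarterly review intervals, and on the DSMP adding no stricter rule. The documents do not allow the number of such events to be estimated; it is probably small. The consequence is a modest gap in committee oversight, not an absence of safety review. It is still worth closing, because the protocol defines this class of SAE itself and the correction is only wording.

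**What to change.** 1. In 8.4.1.2, limit the Grade 1 and Grade 2 lines to non-serious adverse events.
2. In 8.4.1.3, extend the existing 2-working-day line to Grade 1-2 SAEs that are unexpected and at least possibly related, and the existing 5-working-day line to unrelated Grade 1-2 SAEs. Leave the one-working-day line for Grade 5 as it is; a blanket rule for SAEs of any grade would loosen it.
3. In the 8.4.2 table, send unexpected Grade 1-2 SAEs through the existing unexpected Grade 3 columns, with or without hospitalization as applies.
4. In the same edit, state an IRB time frame for expected, related SAEs of all grades. Section 8.4.1.3 currently gives none for expected, related Grade 3-4 events, and no lower-grade SAE should be reported faster than a comparable higher-grade one. Also reconcile the 5 working days in 8.4.1.3 for unrelated Grade 3 events with the periodic review that the 8.4.2 table gives them when there is no hospitalization.
5. Name the recipient of Table 4's 24-hour overdose report, and reconcile that line with the reporting of an overdose that has an adverse event.

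The cost is a few extra expedited report forms and a check that the revised table agrees with the SKCC DSMP. The table carries both Phase I and Phase II rules, so it may be an institutional standard that needs the DSMC's agreement to change. No new visits, data or staff are needed.

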### 8.4.2 Reporting to SKCC DSMC

All AEs and SAEs, safety and toxicity data, and any corrective actions will be submitted to the DSMC per the frequency described in the SKCC DSMP. The report to the SKCC DSMC will also include any unanticipated problems that in the opinion of the PI should be reported to the DSMC.

For expedited reporting requirements, see table below:  
AE/SAE Reporting Requirements

DSMC

	Grade 1	Grade 2		Grade 3				Grades 4 and 5
	Unexpected and Expected	Unexpected	Expected	Unexpected		Expected		Unexpected and Expected
				With Hospitalization	Without Hospitalization	With Hospitalization	Without Hospitalization	
Unrelated Unlikely	Reviewed at Quarterly DSMC Meeting and IRB Annual Review	Reviewed at Quarterly DSMC Meeting and IRB Annual Review	Reviewed at Quarterly DSMC Meeting and IRB Annual Review	5 Working Days	Reviewed at Quarterly DSMC Meeting and IRB Annual Review	5 Working Days	Reviewed at Quarterly DSMC Meeting and IRB Annual Review	Phase I - 48 Hours (Death: 24 Hours) Phase II - 5 working days
Possible Probably Definite	Reviewed at Quarterly DSMC Meeting and IRB Annual Review	Reviewed at Quarterly DSMC Meeting and IRB Annual Review	Reviewed at Quarterly DSMC Meeting and IRB Annual Review	48 Hours (Death: 24 Hours)	Phase I - 48 Hours Phase II - 5 working days	48 Hours (Death: 24 Hours)	Reviewed at Quarterly DSMC Meeting and IRB Annual Review	Phase I and Phase II - 48 Hours (Death: 24 Hours)

#### 8.4.3

### Reporting of Pregnancy

If the female partner of a male patient becomes pregnant during the course of the study, the treating physician must be notified immediately. All confirmed pregnancies must be immediately reported to the medical monitor. All pregnancies will be followed until resolution (i.e., voluntary or spontaneous termination or birth) and assessed for congenital anomalies and birth defects.

### 8.5 Halting Rules

This study will be monitored by the DSMC committee.

Acute toxicity will be monitored using CTCAE version 4.03 criteria during therapy and up to 30-days post completion of surgical resection. If the lowest dose of metformin and doxycycline develop toxicity  $\geq 4$ , the study may be terminated after discussion with PI and sponsor.

## 9 Study Oversight

In addition to the PI's responsibility for oversight, study oversight will be under the direction of the SKCC's Data and Safety Monitoring Committee (DSMC). The SKCC DSMC operates in compliance with a Data and Safety Monitoring Plan (DSMP) that is approved by the NCI.

## 10 Statistical Analysis Plan

### 10.1 General considerations:

All analyses will be performed separately by cohort.

### 10.2 Analysis for primary outcomes.

The primary objective of the study is to assess the impact of metformin and doxycycline on CAV1 expression by immunohistochemistry (IHC) in carcinoma cells. All patients from whom samples are obtained both pre- and post-treatment will be included in the primary analyses. Within-patient change in IHC scores will be analyzed using the Wilcoxon signed-rank test.

### 10.3 Analysis for secondary outcomes.

Analysis of change TOMM20, MCT1, and MCT4 will be performed using the Wilcoxon signed-rank test. Analysis of secondary clinical outcomes will be primarily descriptive. Distribution of progress-free survival and overall survival will be estimated using the Kaplan-Meier method. The objective response rate will be estimated along with an exact 95% binomial confidence interval.

